3.2.3 Secondary Endpoints

The first secondary endpoint is to observe successful conversion of at least one shockable rhythm with a salvo of up to five (5) shocks.

A shock is considered appropriate if the shock is delivered during a period where the subject is experiencing VF or a VT that is considered "life threatening" as defined in the CEC Charter and as adjudicated by the CEC. If multiple successful conversions occur in a single subject, conversions will be counted as separate events only if the rhythm returned to a non-shockable rhythm between conversions (i.e. the Jewel returns to Monitor Mode). All successful conversions will be included in the secondary endpoint analysis. All appropriate shocks and attempted conversions will be reviewed and adjudicated by the CEC and reported.

The second secondary endpoint is to observe a compliance rate of subjects wearing the Jewel of greater than 14.1 average hours per day during a prescription wear period.

3.2.4 Additional Exploratory Analyses

Jewel System Compliance

Subject compliance with using the Jewel system will be evaluated, including average weekly wear.

Detection of Ventricular Arrhythmias

An analysis of all events that trigger the alarm cycle after three (3) consecutive segments of shockable rhythm (~24 seconds in total) will be performed.

Quality of Life

A Quality of Life (QOL) measurement tool (EQ-5D-3L) will be used to quantify any impact that the Jewel has on a subjects QOL.

4. STUDY DESIGN

4.1 Overall Design

This study is a multi-center, prospective, single-arm evaluation of the Jewel P-WCD in adult subjects at risk for sudden cardiac arrest, who are not candidates for or who refuse an implanted cardioverter defibrillator. The study will include up to sixty (60) sites in the United States. This design incorporates one interim analysis at 179 analyzable subjects and one final analysis at 290 analyzable subjects.

There is another analysis point once 100 subjects have completed their prescription wear time, which will be performed to support application for CE mark.

4.2 Scientific Rationale for Study Design

As the patient population being evaluated in this study is at risk for SCA, it would not be ethical to withhold potentially lifesaving defibrillation. Further, the study is designed with a primary endpoint to demonstrate the absence of a rare event (inappropriate shock). For these reasons, a control or placebo arm is not employed in the Jewel IDE study, and all enrolled subjects will receive the study device.

4.3 End of Study Definition

A subject is considered to have completed the study when his or her physician-determined prescription period has ended. The Study Exit Visit will be performed at this time. After study completion, the subject will be asked to return all Jewels and study supplies to the Sponsor. Subject prescription periods may be altered during the course of the study at physician discretion. The end of the study is defined as when the last subject exits the study globally.

5. STUDY POPULATION

5.1 Inclusion Criteria

To be eligible to participate in this study, an individual must meet all of the following criteria:

- 1. Patients of any gender aged \geq 18 years.
- 2. Patients with either:
 - a. a measured LVEF less than or equal to 40% (as assessed by techniques such as, but not limited to, cardiac angiography, echocardiography, magnetic resonance imaging, or radionuclide angiography within the last 30 days prior to enrollment) AND identified as presenting with a diagnosis of an AMI, ischemic cardiomyopathy (includes congestive heart failure: NYHA Class I III), non-ischemic cardiomyopathy, or myocarditis;

OR

b. who have a temporary or long-term contraindication to receiving an ICD, who have had an ICD removed, or who refuse an ICD

OR

c. whose ICD implantation is delayed due to COVID-19 infection or exposure-related risks

5.2 Exclusion Criteria

The opportunity to participate in the study will be offered to all qualifying populations at the Site. An individual who meets any of the following criteria will be excluded from participation in the study:

- 1. Member of a vulnerable patient population as defined in ISO 14155;
- 2. Life expectancy of less than one year, including end-stage heart failure, cancer, or other diagnosed condition;
- 3. Patients with an anticipated initial prescription period over 180 days (limitation only to allow timely closure of this clinical trial);
- 4. Patients with an advanced directive prohibiting resuscitation;
- 5. Existing ICD;
- 6. Existing unipolar pacemaker;
- 7. Existing FDA-cleared or FDA-approved active implantable or body worn medical device(s) that the Sponsor requires to be removed prior to the study but which cannot be removed;
- 8. Clinically significant valve disease, including aortic stenosis, mitral stenosis; mitral regurgitation, tricuspid regurgitation, insufficiency of the aortic or pulmonary valves, any of which is likely to require surgery in the next year;
- 9. A planned procedure, such as Coronary Artery Bypass Graft, within six (6) months;
- 10. End-stage renal disease, or chronic renal failure requiring hemodialysis;
- 11. Planned discharge to an institutional setting with an anticipated stay of greater than seven (7) days;
- 12. Having a mental, visual, physical, or auditory deficit, that could impair their ability to properly place, remove, or interact with the Jewel System;
- 13. Unable to understand English for the purposes of interacting with the device;
- 14. Unable to use a wearable defibrillator due to physical conditions (bandages preventing electrode contact, physical deformities preventing electrode contact, etc.);
- 15. Dextrocardia;
- 16. Body circumference of less than 27 inches or greater than 56 inches in the intended area of the Belt component of the Placement Accessory;
- 17. Participation in an investigational study of a drug, biologic, or device not currently approved for marketing;
- 18. Allergic to or have had a known adverse reaction to medical adhesives or hydrocolloids;
- 19. Active skin breakdown, erythema, or other signs of infection in the pectoral or torso regions where the Adhesive Electrode Patches are applied;
- 20. Females who are pregnant or breast-feeding, or planning to be pregnant in the next 12 months;
- 21. No US-based postal address that can be used to ship and receive study devices and supplies (a Post Office box is **not** an acceptable address for product shipments).
- 22. Patients who, in the opinion of the Investigator, are anticipated to be non-compliant with study instructions;

- 23. Unable to provide or have diminished capacity to provide informed consent;
- 24. Any condition that an Investigator believes would interfere with the intent of the study or make participation not in the best interest of the patient.

5.3 Lifestyle Considerations

During this study, subjects are asked to:

- Prepare their skin prior to each Jewel application. Preparation includes using the provided supplies for skin cleansing and any needed hair trimming.
- Use provided adhesive remover to remove the Jewel from the body and return the used study devices and supplies to the Sponsor using the provided pre-paid shipping materials.
- Wear the Jewel at all times and following instructions for interacting with the device, paying attention to and responding to audio, visual, and vibratory commands. The Jewel should be removed, the Patch Unit replaced, and the Jewel reapplied approximately once per week or as the device directs the subject.
- Try to keep the Jewel out of direct water spray when showering. Study subjects will be told not to submerge the Jewel (i.e., no baths, swimming, hot tubs, etc.).
- Avoid exposing Jewel patches to direct sunlight for more than 5 minutes.
- Avoid operating the Jewel System in hot environments (greater than 50°C /122°F) and cold environments (less than 10°C / 50°F).
- Avoid storing the Jewel System in hot environments (greater than 30°C /86°F) and cold environments (less than 15°C / 59°F).
- Minimize activities that include excessive stretching of the torso or profuse sweating, as such activities will reduce the ability of the device to remain on the skin and may result in the need to replace the Jewel early.
- Bring a back-up Patch Unit and the Placement Accessory when traveling for more than 24 hours.
- Keep cell phones at least 12 inches away from Jewel.

5.4 Screen Failures

Screen failures are defined as subjects who consent to participate in the clinical trial, but who do not subsequently wear a Jewel (Jewel does not enter Monitor Mode). These subjects will not be included in any study analyses. A minimal set of screen failure information will be captured, including demographics, screen failure details, and eligibility criteria.

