1.2 Schema

Screening

- Obtain Informed Consent
- Screen potential subjects by Inclusion and Exclusion Criteria
- Demographics, Medical History, COVID-19 status obtained and documented

Subject Training and Enrollment

- Subject receives Device Training and Placement Accessory Fitting
- Subject places initial Jewel under guidance (Subject is now considered enrolled)
- Subject returns home with the Jewel and an Adhesive Electrode Patch and Battery Unit ("Patch Unit"). NOTE: Element Science may contact the Subject to provide additional training related to the device, product support, and/or information related to the subject's participation in the study at later timepoints.

Prescription Period – as prescribed by Investigator

- Day 2 Phone Call: Follow-up by Element Science to assess any subject support needs.
- Exchange 1- Exchange 4 Follow Up: Office Visit, Telemedicine Visit, or Phone Call: (the first 4 times the subject removes a Jewel and replaces the Patch Unit) collect Patch Unit replacement information/compliance, assessment of patient status, determine if patient needs assistance, training, or supplies from Element Science, determine if new or changes to Adverse Events (AE), medical information, medications; subject completes experience questionnaire. Optional: photographs of device placement.
- Exchange 5 Follow Up through end of prescription period: Office Visit, Telemedicine Visit, or Phone Call: collect Patch Unit replacement information/compliance, assessment of patient status, determine if patient needs assistance, training, or supplies from Element Science, determine if new or changes to AE(s), medical information, medications.

End of Study Assessment (Visit / Phone Call) - within 14 days of device removal

- Adverse Event Review
- Exit Interview
- Study Exit

PR-2053 Rev. E

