8.1.3 Subject Enrollment

If the subject successfully completes device training, site personnel and/or a Sponsor representative will educate the subject on the Jewel to ensure safe and effective use throughout the prescribed duration. If present, caregivers will be invited to participate in all aspects of the training. This training will be performed in a clinical environment.

As part of the training curriculum, the Patient Guide and the Quick Guide, which the subject will take home with him/her, will be utilized to walk a subject through different aspects of the device interaction and care. The Placement Accessory will be custom fit to the subject to aid in applying the device in the correct location. Once the Placement Accessory is fit to the subject, the dimensions are maintained with mechanical rivets and Velcro fasteners which are not intended to be modified by the subject. In the event a subject gains/loses weight, they can contact the study

site who will arrange with Sponsor personnel to refit or replace the Placement Accessory. After the first Jewel is successfully applied to the subject, and the Jewel enters Monitor Mode, the subject will be considered enrolled in the trial.

If the subject has an iPhone 6 or greater and chooses to use the Jewel Mobile Application ("App"), the App will be downloaded to their phone and paired with the Jewel at the time of Enrollment.

The subject will be instructed on whom to call should any device questions arise. The subject will also be instructed to return all used Jewel device supplies back to the Sponsor, using the supplied packaging and pre-paid shipping labels. Site personnel or Sponsor representatives may help facilitate shipping when appropriate.

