3.2. Per Protocol Population

A per-protocol analysis population will be defined as those subjects that are part of the Primary Analysis Population, have worn the Jewel on average for at least 14.1 hours a day, and are without major protocol deviations which may affect the primary safety or effectiveness endpoint measurements. Analyses on the safety and effectiveness endpoints will be repeated on this population.

3.3.Safety Analysis Population

The safety analysis population will consist of all subjects who remain enrolled for longer than 12 hours after the date and time the first Jewel applied to the subject's body transitions to Monitor Mode, regardless of analyzable wear time. For example, if a subject wore the Jewel and subsequently does not return the device or the device was damaged, this subject is still part of the safety analysis population and will be assessed for clinically significant cutaneous Adverse Device Effects.

4. Study Objectives

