7.2. Subject Accountability

Subject accountability will be presented in tabular form. This table will summarize how many subjects were screened and enrolled into this trial. This table will also summarize the number of subjects withdrawing from the study and the reason for withdrawal.

Screen failures are defined as subjects who consent to participate in the clinical trial, but who do not subsequently wear a Jewel (Jewel does not enter Monitor Mode). These subjects will not be included in any study analyses. A minimal set of screen failure information will be captured, including demographics, screen failure details, and eligibility criteria.

8. Sample Size Estimation

A Scientific Literature Review was performed to determine a clinically meaningful rate for inappropriate shocks and safety events. This is documented in the Report of Prior Investigations.

The estimated power for the primary effectiveness endpoint analysis is based off Monte-Carlo simulations. In order to assess power, 10,000 studies were simulated using various study sizes. For each subject within a study, a random wear time was assigned using a normal distribution with an average of 2.5-months and a standard deviation of 0.5 month. Each subject was also assigned a time to inappropriate shock using an exponential distribution. If the time to inappropriate shock is greater than the wear time, then that subject did not experience an event during the course of the trial. If the time to inappropriate shock is less than the wear time, then that subject is considered to have had an event. For subjects experiencing an event, wear time beyond the time to inappropriate shock is in not counted in the simulations. Since inappropriate shock is a rare event, some of the simulated studies had no subjects that experienced an inappropriate shock. When this happened, the study with zero total events was given a total of 0.5 events in order to allow for convergence of the models. Each study was then used to fit a Poisson regression model from which an estimated rate of inappropriate shock along with a one-sided 98% upper bound on that rate was generated. If

that upper bound was below the performance goal, then that study is considered successful, otherwise it is considered to have failed. Adding up the number of successful trials gives an estimate of power for a given sample size.

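### A subject whose Jewel is placed but never enters Monitor Mode is a screen failure left out of every analysis, although the plan promises to tabulate all Adverse Device Effects and its schema counts that subject as enrolled

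*Protocol*

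**What the plan says.** **Screen failure.** Protocol 5.4 covers consented subjects who "do not subsequently wear a Jewel (Jewel does not enter Monitor Mode). These subjects will not be included in any study analyses". The parenthesis equates wearing with reaching Monitor Mode. SAP 7.2 repeats the exclusion: "These subjects will not be included in any study analyses". What is kept is limited: "A minimal set of screen failure information will be captured, including demographics, screen failure details, and eligibility criteria".

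**Enrollment.** Protocol 8.1.3 requires that the first Jewel is successfully applied "and the Jewel enters Monitor Mode, the subject will be considered enrolled in the trial". The schema in Protocol 1.2 sets an earlier point: "Subject places initial Jewel under guidance (Subject is now considered enrolled").

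**Safety population.** SAP 3.3 takes "all subjects who remain enrolled for longer than 12 hours after the date and time the first Jewel applied" moves to Monitor Mode.

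**Safety reporting.** Protocol 3.2.2 and 9.4.2 and SAP 5.3 all state that every ADE will be tabulated. The schedule in Protocol 1.3 marks adverse event evaluation from Exchange 1 onward and leaves the training and enrollment day blank. Protocol 8.2.7 requires all device deficiencies to be reported to the sponsor within three days and gives the DSMB a role in judging their risk.

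**The concern.** Training practice uses a model device (Protocol 8.1.2), but the enrollment step uses the real one. If the real Jewel is adhered and does not start monitoring, the subject has been exposed to the investigational product and the product has not worked. The rule puts that person in the same class as someone who never had a device on the skin. Membership of the safety tables then depends on the device having functioned.

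At stake is the completeness of descriptive safety and device-performance reporting. Protocol 8.2.2 itself lists device failure and non-operation among the anticipated events, yet the earliest such failures have no place in any planned output. Protocol 7.2 also allows consented subjects who are not enrolled to be replaced, so a start-up failure can be followed by a replacement subject without either document planning to show it.

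**Working it through.** **1. Does another provision bring the subject back?** Take a subject with a real Jewel placed that never reaches Monitor Mode.

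- Enrollment (Protocol 8.1.3): not met, because Monitor Mode is required.
- Safety population (SAP 3.3): not met, because its clock starts at the Monitor Mode transition.
- Analyzable wear time (SAP 3.1): none, for the same reason.
- Primary safety event (Protocol 3.2.2): needs permanent withdrawal from the trial by the Investigator. Protocol 7.2 separates consented subjects who are not enrolled from enrolled subjects who are withdrawn, so a never-enrolled subject does not fit.
- ADE, AE and SAE tables (SAP 5.3): the text says all, but SAP 7.2 removes screen failures from any analysis.
- Accountability (SAP 7.2): screened and enrolled counts appear, but no row separates a failed start from an ordinary ineligibility.
- Device deficiencies: neither document plans a table or listing, for any subject.

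Nothing restores the subject.

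**2. Do the documents agree on enrollment?** No. Under Protocol 1.2 this person is enrolled at placement, and Protocol 9.3 then says all enrolled subjects are evaluated on the primary and secondary endpoints. Under Protocol 5.4 and 8.1.3 the same person is a screen failure.

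**3. Effect on the primary effectiveness result.** The rate is first inappropriate shocks divided by analyzable wear time. A subject who never reaches Monitor Mode adds 0 to both, so the rate and its upper limit do not move. The plan's own power figure, about 98% for 290 subjects, reproduces at 98.1% by simulation under SAP section 8 (wear time normal with mean 2.5 and SD 0.5 months, rate 0.37 per 100 subject-months, one-sided alpha 0.02, limit 2.0) and is equally untouched.

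**4. Effect on the 15% safety goal.** SAP 5.3 uses a one-sided 95% Clopper-Pearson upper bound, the 0.95 quantile of Beta(x+1, n−x). Assume n = 290 in the safety set. Then x = 33 (11.4%) gives 14.9% and passes; x = 34 gives 15.3% and fails.

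The number k of excluded subjects is not in the documents. As an extreme case, add k subjects to n and count every one as an event. The smallest k that turns a pass into a miss is:

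| Observed x/290 | Bound as planned | Smallest k | (x+k)/(290+k) | Bound |
|---|---|---|---|---|
| 6 (2%) | 4.0% | 32 | 38/322 | 15.2% |
| 14 (5%) | 7.4% | 23 | 37/313 | 15.3% |
| 23 (8%) | 11.0% | 12 | 35/302 | 15.1% |
| 29 (10%) | 13.4% | 5 | 34/295 | 15.05% |

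If none of the k had an event, adding them would lower the bound: 29/295 gives 13.2% against 13.4% for 29/290.

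**The case against.** The strongest reply is that these failures are not invisible. Deficiency reporting under Protocol 8.2.7 is not restricted to enrolled subjects. The adverse event definition in Protocol 8.2.1 turns on use of the Jewel, not on Monitor Mode. Screen-failure details are collected and would be the natural place for the reason. Some poor-fit cases are properly ineligible under exclusion criteria 14 and 16 or the training assessment in Protocol 8.1.2. All of this stands. It means the loss is in planned outputs, not in everything the sponsor might know. It does not supply a table, nor does it square the exclusion with the promise to tabulate all ADEs.

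Stronger inferences are tempting, but the documents do not support them:

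- *First-application success is 100% by construction.* The rule acts per subject. Nothing bars a second attempt or unit in the same session, and a subject whose later attempt reaches Monitor Mode is enrolled and unaffected. No endpoint reports first-application success.
- *The size can be had by applying a failure rate to the 370 subjects who may be enrolled.* Under Protocol 8.1.3 those subjects have already reached Monitor Mode, so 370 is the wrong denominator, and no failure rate is given. Setting such a count against the few expected inappropriate shocks would also mislead, because these subjects contribute no shocks and no wear time.
- *The primary safety result is materially flattered.* A single supervised placement that never begins monitoring would rarely cause a withdrawal-defining skin event, and leaving out event-free subjects raises the observed rate slightly.

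**Conclusion.** The point holds as a reporting gap and an internal conflict. A subject exposed to the investigational adhesive and electrodes whose device never reaches Monitor Mode is excluded from every planned analysis by an explicit rule in both documents. That rule disagrees with the schema on when enrollment occurs and with the commitment to tabulate all ADEs.

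The number affected is unknown. The effectiveness result does not change. The safety goal would change only if at least 5 such subjects (at a 10% observed rate) to 32 (at 2%) existed and every one counted as an event, which is implausible; the likely effect is negligible. These figures assume 290 subjects in the safety set. What is lost is a clear account of start-up failures and of any ADEs in those subjects. The change is worth making because it is cheap and removes selection on device success from the safety tables.

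**What to change.** 1. Reconcile Protocol 1.2 with Protocol 5.4 and 8.1.3 and SAP 7.2, so that one enrollment point applies throughout.
2. In Protocol 5.4 and SAP 7.2, limit screen failure to subjects on whom no investigational Jewel was placed. The training model device does not count as placement.
3. Add an accountability row for Jewel placed, Monitor Mode not reached, with reasons and with all subjects who had a Jewel placed as denominator.
4. Record adverse events from first placement, mark this in the schedule in Protocol 1.3, and include these subjects in the descriptive AE, ADE and SAE tables of SAP 5.3.
5. Add a short listing of device deficiencies in these subjects.

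Leave the wear-time set and the primary effectiveness analysis as they are; hypotheses, sample size and alpha do not change.

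The cost is edits to a few definitions, adverse event and deficiency forms for what may be a handful of subjects, one accountability row and one new listing. The sponsor may also have to report an application-failure count above zero.
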